### **15.3 Informed Consent**

The investigator, or a person designated by the investigator, will obtain voluntary written informed consent from each subject or the subject's legal representative before any study-specific activity is performed. The investigator must ensure that each study subject, or his/her legal representative, is fully informed about the nature and objectives of the study and possible risks associated with participation. The subject will be given ample time to review the ICF and the opportunity to discuss any questions before making a decision about participation in this study. The process of informed consent will be documented in the subject's source data. The investigator will retain the original of each subject's signed consent document and a signed copy will be provided to the subject.

The informed consent document must be in compliance with ICH guideline on GCPs, the FDA, local regulatory requirements, and legal requirements.

The informed consent document used in this study, and any changes made during the course of the study, must be approved by both the IRB/IEC and Aponia Laboratories, Inc. before use.

#### **15.4 Confidentiality**

All parties will ensure protection of subject personal data and will not include subject names on any sponsor forms, reports, publications, or in any other disclosures, except where required by law.

Subject names, addresses, birth dates, and other identifiable data will be replaced by a numerical code consisting of a numbering system provided by Aponia Laboratories, Inc. in order to de-identify the subjects. In case of data transfer, Aponia Laboratories, Inc. will maintain high standards of confidentiality and protection of subject personal data.

#### **15.5 Reporting of Safety Issues and Serious Breaches of the Protocol or ICH GCPs**

In the event of any prohibition or restriction imposed (ie, clinical hold) by an applicable competent authority in any area of the world, or if the investigator is aware of any new information which might influence the evaluation of the benefits and risks of the investigational product, Aponia Laboratories, Inc. should be informed immediately.

In addition, the investigator will inform Aponia Laboratories, Inc. immediately of any urgent safety measures taken by the investigator to protect the study subjects against any immediate hazard, and of any serious breaches of this protocol or of ICH GCPs that the investigator becomes aware of.

#### **15.6 Access to Records**

The investigator and study personnel will permit study-related monitoring, audits, IRB/IEC review, and regulatory inspections by providing direct access to source data and documents.

#### **15.7 Retention of Records**

To enable evaluations and/or audits from regulatory authorities or Aponia Laboratories, Inc., the investigator agrees to keep records, including the identity of all participating subjects (sufficient information to link records, eg, CRFs and hospital records), all original signed informed consent documents, copies of all CRFs, safety reporting forms, source documents, and detailed records of treatment disposition, and adequate documentation of relevant correspondence (eg, letters, meeting minutes, telephone calls reports).

The investigator must arrange for retention of study records at the site for 2 years after the AP0302 5% New Drug Application is approved or the Investigational New Drug application is withdrawn, as required by FDA regulations. If the investigator becomes unable for any reason to continue to retain study records for the required period (eg, retirement, relocation), Aponia Laboratories, Inc. should be immediately notified. The study records must be transferred to a designee acceptable to Aponia Laboratories, Inc., such as another investigator, another institution, or to an independent third party arranged by Aponia Laboratories, Inc.

The investigator must obtain Aponia's written permission before disposing of any records, even if retention requirements have been met.

### **15.8 Monitoring, Quality Control and Quality Assurance**

During study conduct, Aponia Laboratories, Inc., or its agent will conduct periodic monitoring visits to ensure that the protocol and GCPs are being followed. The monitor will ensure there are no deviations to the informed consent process for all screened subjects. Source data will be reviewed to confirm that there are no deviations to the study protocol and data recorded on CRFs are accurate. The monitor will ensure the following: that essential documents are maintained and IRB approval current; that the study drug is stored appropriately; that drug accountability records are complete and accurate; and that the site's resources remain adequate for the conduct of the trial. The investigator and institution will allow Aponia Laboratories, Inc. monitors or its agents and appropriate regulatory authorities direct access to source documents and all study records to perform this verification.

The study site may be subject to review by the IRB/IEC, to quality assurance audits performed by Aponia Laboratories, Inc., or companies working with or on behalf of Aponia Laboratories, Inc., and/or to inspection by appropriate regulatory authorities.

It is important that the investigator(s) and their relevant personnel are available during the monitoring visits and possible audits or inspections and that sufficient time is devoted to the process.

### **15.9 Sponsor Discontinuation Criteria**

Premature termination of this study may occur because of a regulatory authority decision, change in opinion of the IRB/IEC, drug safety problems, or at the discretion of Aponia Laboratories, Inc. In addition, Aponia Laboratories, Inc. retains the right to discontinue development of AP0302 5% at any time.

If a study is prematurely terminated or discontinued, Aponia Laboratories, Inc. will promptly notify the investigator. After notification, the investigator must contact all participating subjects

[figure not shown]
and the pharmacy (if applicable) within 14 days. As directed by Aponia Laboratories, Inc., all study materials must be collected and all CRFs completed to the greatest extent possible.

## **16 PUBLICATION OF STUDY RESULTS**

[figure not shown]
Please refer to the Clinical Study Agreement for the details and requirements for investigators interested in publishing the results of this study.

**Appendix 1 Schedule of Assessments**

	Screening Visit	Exercise Visit	Treatment Period				Follow-up Phone Call
	Day-28 to Day -3	Day -2 or -1	CBI				Day 7 ±1 day
Informed consent	X						
Verify/re-assess eligibility	X	X	X				
Demographics	X						
Medical history	X	X	X				
Exercise history	X	X					
Record height and weight	X						
Record prior/current medications and non-medicinal therapies	X	X	X	X	X	X	X
Physical examination	X					X	
Physical examination – abbreviated/symptom directed only based on Screening 		X					
Vital signs (BP, HR, temperature, and RR)	X	X	X			X	
12-lead ECG	X					X	
Clinical laboratory tests (chemistry, hematology, coagulation, and urinalysis)	X					X	
Urine drug screen/ Alcohol breath test	X	X	X				
Pregnancy test (WOCBP)	X	X	X				
CBI	X						
Exercise regimen		X					
CBI			CBI				
Muscle pain/soreness with movement Categorical Pain Rating Scale 			CBI				
PI-NRS, Muscle stiffness with movement NRS 			CBI				
Relief from starting pain with movement Categorical Relief Rating Scale 				X			
Subject’s global assessment of study medication 						X	
Adverse events				X	X	X	X

Abbreviations: BP = blood pressure; ECG = electrocardiogram; HR = heart rate; NRS = numerical rating scale; PI-NRS =Pain Intensity Numerical Rating Scale; RR = respiratory rate; T0 = time of first application of study drug; WOCBP = women of childbearing potential.

## Appendix 2 NRS and Categorical Rating Scales

### PAIN INTENSITY NUMERICAL RATING SCALE

What number represents your muscle pain/soreness with movement?

No Pain 0 1 2 3 4 5 6 7 8 9 10 Worst Possible Pain

### CATEGORICAL PAIN RATING SCALE

What word best describes your muscle pain/soreness with movement?

- None (0)
- Slight (1)
- Moderate (2)
- Severe (3)

### MUSCLE STIFFNESS NUMERICAL RATING SCALE

Stiffness refers to how hard it is to flex and extend your arm.

What number represents your muscle stiffness with movement?

No Stiffness 0 1 2 3 4 5 6 7 8 9 10 Worst Possible Stiffness

### CATEGORICAL RELIEF RATING SCALE

What word best describes your relief from starting pain?

- No relief (0)
- A little relief (1)
- Some relief (2)
- A lot of relief (3)
- Complete relief (4)

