#### Post-Exercise:

7.

CBI

“moderate” on a Categorical Pain Rating Scale using the words “none” “mild,” “moderate,” or “severe.”

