#### 10.1.4 Categorical Relief Rating Scale

Subjects will rate relief from starting pain with movement using a 5-point categorical relief scale: “no relief,” “a little relief,” “some relief,” “a lot of relief,” or “complete relief.”

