### 10.2.3 Other Secondary Endpoints:

- Sum of time-weighted differences from baseline in muscle stiffness with movement (SSIDMOVE) over the following intervals: 0-6, 6-12, 0-12, 12-24, 0-24, 0-36, 24-48, and 0-48 hours post-T0.
- Total relief with movement (TOTPARMOVE) over 0-6 hours post-T0.
- Subject's global assessment of study medication assessed at approximately 48 hours post-T0 (or upon early termination, if applicable).

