### 11.3 Treatment Period Visit (Days 1 to 3)

[figure not shown]
CBI

CBI. The following assessments and procedures will be performed to determine eligibility:

[figure not shown]
- Eligibility will be re-assessed.
- Update medical history. Changes in health between the Screening Visit until the Treatment Period Visit, prior to the first dose of study medication, will be captured as medical history.
- Review prior/current medications and non-medicinal therapies.
- Vitals signs (blood pressure, heart rate, temperature, and respiratory rate) will be collected after the subject has been seated for at least 5 minutes.
- Obtain urine for a urine drug screen. Results should be reviewed prior to treatment with IP.
- Perform the alcohol breath test. Results should be reviewed prior to treatment with IP.
- Obtain sample for urine pregnancy test in WOCBP. Results should be reviewed prior to treatment with IP.

CBI

CBI

CBI

- The following assessments are to be completed at CBI [REDACTED], CBI [REDACTED] post first dose of IP and immediately prior to the subsequent doses of IP:
  - Muscle pain/soreness with movement on the PI-NRS
  - Muscle Stiffness with movement on the Muscle Stiffness NRS

- The following assessment is to be completed at [REDACTED] post first dose of IP and immediately prior to a subsequent dose of IP, if one occurs prior to [REDACTED]
  - Relief from starting pain with movement on the Categorical Relief Rating Scale
- [REDACTED].
- At approximately [REDACTED] post-T0, the Subject Global Assessment of IP will be recorded in addition to the [REDACTED] NRS assessments.
- [REDACTED]
- Record any AEs and any concomitant medications or non-medicinal therapies throughout the visit.

On Day 3, at approximately [REDACTED] post-T0, the following assessments and procedures will be performed:

- [REDACTED]
- Perform a physical examination [REDACTED].
- Record vital sign measurements (blood pressure, heart rate, temperature, and respiratory rate) after subject has been in a seated position and resting quietly for at least 5 minutes.
- Perform 12-lead ECG with the subject in a supine position after subject has been resting quietly for 10 minutes.
- Obtain laboratory tests as follows:
  - Obtain blood and urine for laboratory tests (multiphasic chemistry, hematology, coagulation, and urinalysis).
- Any AEs and concomitant medications or non-drug therapies will be recorded.

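### The relief question printed in Appendix 2 does not state the movement condition that the TOTPAR-with-movement endpoint requires

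*Combined protocol and SAP*

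**What the plan says.** The body of the protocol is consistent on the relief measure. Section 10.1.4 defines it: "Subjects will rate relief from starting pain with movement using a 5-point categorical relief scale". Section 10.2.3 names the endpoint "Total relief with movement" and sets its window at 0-6 hours after T0. Section 11.3 lists the procedure as "Relief from starting pain with movement on the Categorical Relief Rating Scale". The Appendix 1 row reads "Relief from starting pain with movement Categorical Relief Rating Scale". The Synopsis and Section 8 say the same.

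Appendix 2, which prints the items that subjects answer, words the relief item as "What word best describes your relief from starting pain", with no movement condition. The pain item in the same appendix reads "What number represents your muscle pain/soreness with movement", and the categorical pain and stiffness items also carry the condition.

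On the entry scale, the legible part of Inclusion 7 (Section 8.1.1, Post-Exercise) names the moderate level "on a Categorical Pain Rating Scale using the words" none, mild, moderate or severe. Section 10.1.2 lists the same four words. The Appendix 2 form prints None, Slight, Moderate and Severe.

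**The concern.** Appendix 2 is the data-collection instrument, so its wording decides what is recorded. A subject who meets the qualifier on the pain and stiffness questions and does not find it on the relief question may judge relief for the arm at rest, or overall. Such a rating is not relief with movement, yet it would enter TOTPAR-MOVE as if it were. At stake is how cleanly one other secondary endpoint can be interpreted, and whether it can be read alongside SPID-MOVE 0-6 hours, which covers the same window and rests on an item that does state the condition. A rating given to an ambiguous question cannot be reclassified afterwards, so the time to act is before the forms are issued.

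The entry-scale labels are a smaller matter of the same kind: Inclusion 7 specifies the words of its scale, and the printed form does not carry all of them.

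**Working it through.** The plan gives no figure on this point, so the check is a comparison of texts.

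**Symptom items in Appendix 2: is the movement condition printed?**

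- Pain Intensity NRS: yes.
- Categorical Pain Rating Scale: yes.
- Muscle Stiffness NRS: yes.
- Categorical Relief Rating Scale: no.

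One of the four symptom questions lacks it. The omission is therefore not the house style of the appendix.

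**Relief measure elsewhere: is the movement condition stated?**

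- Synopsis and Section 8, assessment lists: yes.
- Section 10.1.4, scale definition: yes.
- Section 10.2.3, endpoint: yes.
- Section 11.3, procedure: yes.
- Appendix 1, schedule row: yes.

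The five relief categories agree between Section 10.1.4 and Appendix 2. Only the stem of the question differs.

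**Could other text close the gap?** Section 10.1 says that subjects are trained on the scales, and it points to Appendix 2 and a separate reference document. Its legible sentence mentions movement for none of the scales, so it settles nothing either way. The text that follows it, the PI-NRS instructions in Section 10.1.1 and the order of procedures in Section 11.5 are redacted.

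**Direction and size.** Section 14.4.3 builds TOTPAR as a weighted sum of the relief ratings, so a shift in the mean rating carries through in proportion. Let d_M be the treatment difference in mean relief when rated with movement, d_R the difference when rated otherwise, and p the share of ratings given otherwise, taken as equal in both arms and constant over time. Then

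observed difference = (1 − p) × d_M + p × d_R,

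and the proportional loss is p × (1 − d_R / d_M). The loss is zero if p = 0 or if d_R = d_M. The documents give none of the three quantities. Purely to show the form, assume d_M = 0.5 and d_R = 0.1 of a category:

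- p = 0: 0.50, no loss.
- p = 0.25: 0.75 × 0.5 + 0.25 × 0.1 = 0.40, a loss of 20%.
- p = 0.50: 0.50 × 0.5 + 0.50 × 0.1 = 0.30, a loss of 40%.

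These values are assumptions, not estimates for this trial.

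**Entry scale.** Three of the four labels agree (none, moderate, severe). The second differs: *mild* in Inclusion 7 and Section 10.1.2, *Slight* in Appendix 2. The label at the level named in the legible criterion, moderate, is the same in both places.

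**The case against.** The strongest defence is that the intended meaning is clear in context. The legible baseline ratings are all made with movement, and no legible section collects a pain score at rest, so starting pain most naturally means the movement-rated baseline. The scale definition, procedures and schedule all require the rating with movement, subjects are trained, and redacted text may already place the relief rating straight after a prescribed movement. The same form is used in both blinded arms, so nothing points to bias in favour of either. TOTPAR 0-6 hours is only one of the other secondary endpoints.

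Most of this stands. A reader might infer that the form fails to measure the declared endpoint; the documents do not support that, for the reasons just given. Nor do they support expecting a loss of 20% or 40%, since every input to those figures is assumed. What remains is narrower. Starting pain identifies the reference point, but it does not say whether present relief is judged while moving or at rest. The instruction that would settle this is not in the item and cannot be seen in the legible text.

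A reader might also infer that *Slight* pushes subjects with milder soreness up to *Moderate* and so into the trial. Nothing in the documents shows that subjects would choose that way. The text around the moderate level in Inclusion 7 is redacted, so the full rule cannot be read.

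**Conclusion.** The point holds in limited form. The printed relief item does not itself carry the movement condition that the scale definition, endpoint, procedures and schedule require, and it is the only symptom item in Appendix 2 without it. The tie to TOTPAR-MOVE 0-6 hours therefore rests on training or instructions outside the item. If some subjects rate relief at rest or overall, and if the treatment difference is smaller there, the TOTPAR difference is diluted. The amount is unknown, and it is zero if training leads every subject to rate with movement. The primary SPID-MOVE, and the key secondary SPID-MOVE intervals built on the same pain item, are not affected.

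The *Slight*/*mild* mismatch is certain as a matter of text, but it is a minor inconsistency with no demonstrable effect on eligibility.

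**What to change.** Before the forms or electronic screens are issued, add the words *with movement* to the Appendix 2 relief question so that it matches Section 10.1.4. At the same time, reconcile the second label of the categorical pain scale across Inclusion 7, Section 10.1.2 and Appendix 2, so that one word is used throughout.

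The cost is two wording edits. Neither adds an assessment or changes the sample size or the analysis, and there is no drawback if they are made before the first subject is enrolled.

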**SUBJECT GLOBAL ASSESSMENT**

Overall, how would you rate the investigational product you received?

- Poor (0)
- Fair (1)
- Good (2)
- Very Good (3)
- Excellent (4)

CBI

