### **8.1.2 Exclusion Criteria**

1. Subjects who have regularly worked out or exercised the upper extremities with weights or gym equipment during the past 3 months.
2. Subjects who have a job or hobby that involves regular lifting or involvement of the upper extremities (eg, rock climbers, movers, construction workers).
3. Subjects with a history of surgery, significant trauma, significant musculoskeletal pathology, or significant nervous system pathology in the neck or in the non-dominant arm or shoulder that is likely to be exacerbated by the exercise regimen, in the opinion of the investigator.
4. Subjects with any condition, in the investigator’s judgment, that may interfere with local tolerability assessments in the area of study drug application, including recently applied tattoos.
5. History of any muscle disorder (eg, statin myopathy or any muscular dystrophy), neuropathy, fibromyalgia, rhabdomyolysis, or chronic fatigue syndrome.
6. Presence of another painful physical condition that, in the opinion of the investigator, may confound study assessments.
7. Any contraindication to the use of ibuprofen, or any nonsteroidal anti-inflammatory drug (NSAID) or cyclooxygenase-2 inhibitor, or aspirin, including any history of asthma or recent history of gastritis or gastrointestinal bleeding.
8. Presence of an allergy or intolerance to any NSAID or aspirin or any of the components of the study drug.
9. Presence of a latex allergy (customized armband components contain latex).
10. Any skin condition that could potentially interfere with absorption of drug (eg, keloid, rash, dermatitis).
11. Have received chronic opioid therapy defined as greater than 15 morphine equivalents units per day for greater than 3 out of 7 days per week in any 1-month period within 12 months prior to Day 1.
12. Have received an opioid within 30 days prior to Day 1.
13. Routine use (defined as 3 out of 7 days per week) of any analgesic drug (OTC or prescription).

14. Consumption of any medication (prescription or OTC medications, vitamins, minerals, and dietary supplements) within 2 weeks prior to Day 1. Exception: continuing hormonal contraception and hormone replacement therapy is allowed.
15. Any history of drug or alcohol abuse (according to the investigator's judgment) in the prior 5 years.
16. The subject has received an investigational drug or device within 3 months prior to screening.

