#### **9.4 Blinding**

This is a double-blind, randomized study. The sponsor, site staff and subjects will be blinded as to whether each tube of IP contains active treatment or vehicle. The study blind may be broken for a specific subject only in the event of a medical emergency and when a decision regarding the subject's condition requires knowledge of the treatment assignment. Any such cases will be clearly justified and explained in a note to file. The investigator will notify the Aponia medical monitor immediately in the event of the situation.

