#### 14.4.3 Other Secondary Analyses

The following other secondary endpoints for different time intervals will be compared between the 2 treatment groups using an ANCOVA model with the baseline pain/soreness score as the covariate.

- $SSID_{MOVE}$  over the following intervals: 0-6, 6-12, 0-12, 12-24, 0-24, 0-36, 24-48, and 0-48 hours post- $T_0$ . The mean  $SSID_{MOVE}$  for 0-6, 6-12, 0-12, 12-24, 0-24, 0-36, 24-28, and 0-48 hours post- $T_0$  will be compared between the 2 treatment groups (active versus vehicle) using an ANOCVA model with the baseline muscle stiffness score as the covariate.
- $TOTPAR_{MOVE}$  over 0-6 hours post- $T_0$ . An ANOVA model will be used for these efficacy endpoints.

$TOTPAR_{MOVE}$  A-B hr =  $\sum_{i=A}^{B-1} PR_i H$  where  $i$  refers to each pain relief scheduled assessment time point between A and B (not including B).

The TOPAR endpoints will be compared between the 2 treatment groups using an ANOVA model.

The subject's global assessment of efficacy will be assessed at approximately 48 hours post-T0 (or upon early termination if the subject withdraws prior to the 48-hour assessment). The distribution of 5 categories (poor, fair, good, very good, or excellent) will be compared between the 2 treatments (active versus vehicle) using the Chi-Squared test. In addition, the 5 categories will be dichotomized into 2 categories (good/very good/excellent versus poor/fair). The proportion of good, very good, and excellent ratings will be calculated for each treatment. This proportion will be compared between the 2 treatments (active versus vehicle) using the Fisher's Exact test.

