#### **14.5 Safety Analysis**

For the safety analysis, descriptive statistics such as mean, median, minimum, maximum, and standard deviation will be summarized for continuous variables. Frequency distributions will be summarized for categorical variables. Since all subjects will receive vehicle on the dominant arm in addition to blinded study drug on the non-dominant arm, some subjects will receive both active and vehicle treatments. All safety-related data will be summarized as an overall group except AEs related to the area of application.

Adverse events will be coded using the Medical Dictionary for Regulatory Activities (MedDRA) version 19.1 (or higher). For summary tables, AEs coded to the same preferred term will be counted only once within a given subject. If an AE was recorded on multiple occasions in the same treatment period, only the highest severity and the highest degree of relationship to the study drug will be presented. If 2 or more clinical events are reported within a single AE entry, then the corresponding individual preferred terms will be coded separately.

All AEs, including those that are not treatment-emergent, will be listed. All summaries of AEs will be of TEAEs. A TEAE is defined as an AE that is new or worsened in severity after the first dose of study drug. Adverse events will be summarized by system organ class (SOC), and preferred term. Summaries will be prepared for all AEs, treatment-related AEs, and SAEs. The AE summary will also be presented with a breakdown by severity. Adverse events that are specific to the arm, such as application site reactions, will be summarized by treatment (active versus vehicle).

Changes from baseline in chemistry, hematology, coagulation, and urinalysis parameters will be summarized descriptively. Laboratory results will be classified as low, normal, or high according to the laboratory-supplied reference ranges. Shift tables describing out-of-range shifts from

baseline (in frequency counts) will be created and presented by treatment. All laboratory results will be listed.

The results of physical examinations will be summarized by body categories with frequency and percentages of normal versus abnormal, and if abnormal whether it is clinically significant or non-clinically significant. A listing of physical examination results will be presented by subject and assessment time point.

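### The printed Subject Global Assessment does not name the arm being rated, so the active-versus-vehicle difference on this other secondary endpoint may be biased toward zero

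*Combined protocol and SAP*

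**What the plan says.** The item is printed in full, in the same words, in 10.1.5 and in Appendix 2: "Overall, how would you rate the investigational product you received". Five answers follow, from poor (0) to excellent (4). Neither place names an arm, a tube or an application site.

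Section 14.5 describes what subjects are given: "Since all subjects will receive vehicle on the dominant arm in addition to blinded study drug on the non-dominant arm". It draws the consequence itself: "some subjects will receive both active and vehicle treatments". For that reason it summarises arm-specific adverse events by treatment.

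Section 9.4 says that sponsor, staff and subjects are "blinded as to whether each tube of IP contains active treatment or vehicle". As used there, the term IP can apply to a tube of either content.

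Section 10.2.3 lists the rating last among the other secondary endpoints, taken at about 48 hours or at early termination, and calls it an assessment of study medication. Section 14.4.3 calls it an assessment of efficacy. The five categories are compared by chi-squared test and then dichotomised as good or better versus poor or fair: "This proportion will be compared between the 2 treatments (active versus vehicle) using the Fisher's Exact test".

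**The concern.** The analysis takes the answer as a rating of the product to which the subject was randomised. In the vehicle group this is safe whichever arm the subject has in mind, since both arms carry vehicle. In the active group it is not guaranteed. The question asks for one overall rating of a product in the singular, while the subject has had two blinded-looking applications and cannot tell from the term IP which one is meant.

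An active-group subject who blends the two, or answers for the dominant arm, is partly rating vehicle. If active does better than vehicle, each such answer moves the active group toward the vehicle group. What is at stake is sensitivity on one named secondary endpoint.

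**Working it through.** **Plan's own figure.** Section 14.3 gives 250 subjects, 125 per group. The effect size, standard deviation and power behind that number are redacted, so it cannot be reproduced. The visible text gives no response rate or power for the global assessment.

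**Inputs from the documents.** n = 125 per group (14.3); 1:1 allocation (14.2); two-sided 0.05 (14.4); dichotomised comparison of good or better (14.4.3).

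**Assumed inputs, not in the documents.** Proportion good or better when the randomised product is rated: pA = 0.60 on active, pV = 0.40 on vehicle. Share q of active-group subjects who in effect rate vehicle: 0, 0.10, 0.25, 0.50. Those subjects are assumed to answer at the rate pV.

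**Step 1: the difference.** The active proportion becomes p = (1 − q)·pA + q·pV = 0.60 − 0.20q, so the difference is (1 − q)(pA − pV) = 0.20(1 − q).

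**Step 2: power, normal approximation with pooled null variance.** With p̄ = (p + pV)/2, SE0 = √(2p̄(1 − p̄)/125) and SE1 = √([p(1 − p) + pV(1 − pV)]/125), power = Φ((p − pV − 1.96·SE0)/SE1).

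At q = 0: SE0 = √(0.50/125) = 0.06325 and SE1 = √(0.48/125) = 0.06197. Then (0.20 − 0.12396)/0.06197 = 1.227, and power is 0.890.

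| q | Active p | Difference | Power (normal) | Power (Fisher, exact enumeration) |
|---|---|---|---|---|
| 0 | 0.60 | 20 points | 0.890 | 0.864 |
| 0.10 | 0.58 | 18 points | 0.816 | 0.780 |
| 0.25 | 0.55 | 15 points | 0.663 | 0.615 |
| 0.50 | 0.50 | 10 points | 0.355 | 0.306 |

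**Step 3: other rates.** With 50% versus 65%, the difference at the same four values of q is 15, 13.5, 11.3 and 7.5 points. Power is 0.671, 0.578, 0.432 and 0.220 (Fisher 0.619, 0.523, 0.379, 0.183).

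**Step 4: type I error.** At q = 1 the two groups have the same response rate. Fisher's test then rejects in about 3.6% of trials at a common rate of 40%, and 3.7% at 50%. Both are below 5%, so misattribution does not inflate the error rate.

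**Step 5: how far the rate assumed for misdirected answers matters.** The dominant arm appears not to be exercised, so answers about it could follow some other rate pD. If the same share q in both groups rates the dominant arm, the difference is [(1 − q)pA + q·pD] − [(1 − q)pV + q·pD] = (1 − q)(pA − pV). The shrinkage factor does not depend on pD, although the power figures would change.

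**The case against.** The strongest reply is that subjects will rate the sore arm without being told to. Exclusion criterion 3 (8.1.2) concerns pathology "in the non-dominant arm or shoulder that is likely to be exacerbated by the exercise regimen", and section 9.7.2 bars heat and ice only on the non-dominant arm. By 48 hours the subject has repeatedly rated pain, stiffness and relief from starting pain. This stands in part: it makes a low q plausible, and q = 0 is compatible with the documents. It does not settle the matter, because the item asks for an overall product rating and mentions neither pain nor relief. Tolerability or the feel of the gel on either arm could enter the answer.

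Second, section 14.5 itself separates dominant-arm vehicle from blinded study drug, and the general blinding sentence in 9.4 does not say that the dominant-arm tube is IP. Also, 9.1, 9.3 and parts of 10.1 and 11.3 are redacted, and 10.1 points to a separate reference document. The other Appendix 2 items name no arm either, so the arm may be set by instruction. This stands: one cannot say that subjects receive no direction. The printed question is nevertheless visible in both places and silent on the arm.

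A reader might infer that the rating is not tied to the randomised treatment, or that dilution is established. The documents support neither. The non-dominant-arm product is the only planned difference between the groups, so a treatment effect on the rating comes from the randomised product. No passage shows that anyone rates the dominant arm.

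**Conclusion.** This is a cheap improvement, not an error in the plan. The comparison in 14.4.3 is a valid randomised one without type I inflation. The possible harm is a bias toward zero and a loss of power, and it arises only if active outperforms vehicle and some active-group subjects rate both applications or the dominant arm.

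The proportional loss in the difference equals the misattributed share under the model used. The documents give no basis for choosing that share or the response rates, so the power figures are illustrative. Importance is low: the item is the last-listed other secondary endpoint, and the primary SPID over 0-24 hours does not draw on it.

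**What to change.** In 10.1.5 and Appendix 2, reword the item to: *Overall, how would you rate the investigational product applied to your non-dominant (exercised) arm?* Check the wording against the unredacted dosing and rating instructions, so that the item and any existing direction to subjects agree.

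The change is one phrase made before the questionnaire is used. It adds no assessment and leaves the analysis and the blinding as they are. The downside is a slight departure from the generic global-assessment wording.
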